## 13.0 Allowances for the 'Rescue Study' Transition

### 13.1 Legacy Data

This study is a "rescue study," actively in conduct and recruiting subjects. The database that was originally used to collect patient data was Medrio, and was managed by Hammersmith Medicines Research Ltd (HMR), under a separate contract with Altimmune. The Medrio database collected patient data up to and including Version 5 (Amendment 4) of the protocol prior to the date of transition, November 30th 2016. The Medrio database contained information on 17 subjects (15 enrolled and 2 screen failures) in Cohort 1, at various stages of completion up until the date of transition given above. For more information please consult the data management plan.

PRA have designed the eCRF in compliance and accordance with Version 6 (Amendment 5) of the protocol dated 11-AUG-2016, upon which this SAP is based, and any future updates to Version 6 (Amendment 5).

Any previously collected data in Medrio that was not specifically required to be collected under previous protocol versions will not be collected by PRA, and will not be transcribed into the PRA database, but will

remain in the original database. These types of data include, free text fields, and ECG specific parameters. PRA will request from HMR SAS datasets of the historic legacy data to enable the creation of consolidated SDTM datasets for programming and analysis.

The data that were collected on previous eCRFs not maintained by PRA and not required by protocol, will be placed in a separate listing for each individual subject and will not contribute to any summary tables.

## 14.0 Allowances for Missing Data

Other than the parameters described in this section, no further imputation for missing data will be performed.

### 14.1 Immunogenicity

Any laboratory, immunogenicity or virology data that are below the limits of quantification will be imputed to one-half of the lower limit of quantification (LLOQ) for quantitative summaries and analyses.

### 14.2 Missing Date and Time Information for Prior or Concomitant Medications

#### 14.2.1 Incomplete Start Date

The following rules will be applied to impute the missing numerical fields. If the stop date is complete and the imputed start date is after the stop date, then the start date will be imputed using the stop date.

##### 14.2.1.1 Missing day, month and year

- The day, month and year of the date of the first dose of investigational product will be assigned to the missing fields.

##### 14.2.1.2 Missing day and month

- If the year of the incomplete start date is the same as the year of the date of the first dose of investigational product, then the day and month of the date of the first dose of investigational product will be assigned to the missing fields.
- If the year of the incomplete start date is before the year of the date of the first dose of investigational product, then December 31 will be assigned to the missing fields.
- If the year of the incomplete start date is after the year of the date of the first dose of investigational product, then 01 January will be assigned to the missing fields.

##### 14.2.1.3 Missing day only

- If the month and year of the incomplete start date are the same as the month and year of the date of the first dose of investigational product, then the day of the date of the first dose of investigational product will be assigned to the missing day.
- If either the year is before the year of the date of the first dose of investigational product or if both years are the same but the month is before the month of the date of the first dose of investigational product, then the last day of the month will be assigned to the missing day.
- If either the year is after the year of the date of the first dose of investigational product or if both years are the same but the month is after the month of the date of the first dose of investigational product, then the first day of the month will be assigned to the missing day.

#### 14.2.2 Incomplete Stop Date

The following rules will be applied to impute the missing numerical fields. If the imputed stop date is

before the start date (imputed or non-imputed start date), then the imputed stop date will be equal to the start date.

#### 14.2.2.1 Missing day, month and year

- The day, month and year of the date of the last dose of investigational product will be assigned to the missing fields.

#### 14.2.2.2 Missing day and month

- If the year of the incomplete stop date is the same as the year as of the date of the first dose of investigational product, then the day and month of the date of the first dose of investigational product will be assigned to the missing fields.
- If the year of the incomplete stop date is before the year of the date of the first dose of investigational product, then 31 December will be assigned to the missing fields.
- If the year of the incomplete stop date is after the year of the date of the first dose of investigational product, then 01 January will be assigned to the missing fields.

#### 14.2.2.3 Missing month only

- If the day and year of the incomplete stop date are the same as the day and year of the date of the last dose of investigational product, then the month of the date of the last dose of investigational product will be assigned to the missing month.
- If the day and year of the incomplete stop date are not the same as the day and year of the date of the last dose of investigational product, then December will be assigned to the missing month.

#### 14.2.2.4 Missing day only

- If the month and year of the incomplete stop date are the same as the month and year of the date of the last dose of investigational product, then the day of the date of the first dose of investigational product will be assigned to the missing day.
- If either the year is before the year of the date of the last dose of investigational product or if both years are the same but the month is before the month of the date of the first dose of investigational product, then the last day of the month will be assigned to the missing day.
- If either the year is after the year of the last dose of investigational product or if both years are the same but the month is after the month of the date of the first dose of investigational product, then the first day of the month will be assigned to the missing day.

#### 14.2.3 Incomplete Start Time

If the start time is missing then if the start date (or imputed start date) is the same as the date of dose, then set to the time of dose. Otherwise, set missing start times to 00:00.

#### 14.2.4 Incomplete Stop Time

If the stop time is missing then set it to 23:59.

### 14.3 Missing Date and Time Information for Adverse Events

For AEs, only incomplete (i.e., partially missing) start dates and times will be imputed.

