6 ELIGIBILITY CRITERIA

6.1 Inclusion criteria

1. Male and female subjects aged 18-65 years.
2. Diagnosed with CHB defined as HBsAg positive for at least 24 months.
3. Subject has received entecavir or tenofovir for at least 2 years with a stable dose for at least 6 months prior to screening.
4. HBeAg negative for at least 2 years prior to inclusion in the study.
5. HBV DNA <50 IU/mL for \geq 12 months
6. ALT or AST \leq 1.5 x the ULN via the local laboratory at the Screening Visit
7. Able to give written informed consent to participate
8. Females should fulfil one of the following criteria:
 - a. At least one year menopausal
 - b. Surgically sterile
 - c. Same-sex relationship
 - d. Women of childbearing potential not surgically sterilised or with laboratory confirmed menopausal status are required to use a highly effective contraceptive measure with low used dependency such as:
 - o Combined (oestrogen- and progestogen-containing) hormonal contraception associated with inhibition of ovulation
 - o Progestogen-only hormonal contraception implants associated with inhibition of ovulation
 - o Intrauterine device (IUD)
 - o Intrauterine hormone-releasing system (IUS)
 - o Bilateral tubal occlusion
 - o Vasectomised partner – must have had medical assessment of successful surgery.

From screening until one menstrual cycle after the last dose of IMP (Day 57).

Subjects who practice true abstinence or who exclusively have same sex partners need not use contraception, provided it is in line with their preferred and usual lifestyle. Periodic abstinence (eg, calendar, ovulation, symptothermal, post-ovulation methods) and withdrawal are not acceptable methods of contraception. Should any such subject stop practicing true abstinence, they must use contraception as described above.

Males should fulfil one of the following criteria:

- Surgically sterile
- Willing to abstain from sexual intercourse or use a reliable form of contraception (e.g. condom with spermicide), if having sex with a pregnant or non-pregnant woman of childbearing potential, from screening until 3 months after the final dose of IMP.
- Surgically sterilised or post-menopausal female partner or same-sex relationship

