### 12.3.2 Concomitant Medications

Version WHO DDE B2 Mar\_2017 of the WHO Drug Dictionary will be used to classify prior and concomitant medications by preferred term.

Prior medication is defined as any medication with the start date and time prior to the date and time of the first dose of investigational product. All prior medication will be recorded on the appropriate eCRF page.

Concomitant medication refers to all treatments taken at any time from the date and time of the first dose of investigational product through 30 days after the last dose of investigational product. It is possible for a medication to be considered both prior and concomitant. For instance, a medication that begins prior to the first dose of investigational product and continues during the study.

Concomitant medications will be coded to Anatomical Therapeutic Chemical (ATC) group (level 2) and preferred term. For summaries, multiple medication usage by a subject in the same ATC level or preferred term category will be counted only once.

For the Day 85 analysis the following summary will be presented for the Safety Analysis Set by treatment group:

- All concomitant medications by preferred term.

For the Day 225 analysis the following summaries will be presented for the Safety Analysis Set by treatment group:

- Concomitant medications that were started prior to first dose of investigational product and continued after the first dose of investigational product (i.e., medications that are considered both prior and concomitant) by ATC level 2 and preferred term
- Concomitant medications that were started on or after the first dose of investigational product by ATC level 2 and preferred term.

All prior and concomitant medication for individual subjects will be listed.

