#### 14.3.1 Incomplete Start Date and time

Follow same rules as in [section 14.2.1](#) and [section 14.2.3](#).

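### SAP 14.3 and 14.3.1 conflict on adverse events with no start date, 14.2.1 has no rule for a missing month, and medicines recorded at screening without a start date are dated to the first injection

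*SAP*

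**What the plan says.** **Adverse events.** SAP 14.3 limits the scope: "For AEs, only incomplete (i.e., partially missing) start dates and times will be imputed". SAP 14.3.1 then gives the method: "Follow same rules as in" sections 14.2.1 and 14.2.3, with no part of either excluded. SAP 14.0 rules out any imputation beyond what section 14 describes.

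**The imported rules.** SAP 14.2.1 is headed as dealing with incomplete start dates, but its first rule, 14.2.1.1, covers a date with nothing known: "The day, month and year of the date of the first dose of investigational product will be assigned to the missing fields". A guard protects records whose stop date is known in full; it applies when an "imputed start date is after the stop date, then the start date will be imputed using the stop date". For a missing time, 14.2.3 turns on the start day, whether recorded or imputed: where that "is the same as the date of dose, then set to the time of dose. Otherwise, set missing start times to 00:00". Where only the year is known and it "is before the year of the date of the first dose of investigational product, then December 31 will be assigned to the missing fields" (14.2.1.2).

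**Where the dates are used.** SAP 12.6.1 defines a TEAE by onset or worsening after the first dose, up to 30 days after the last. SAP 12.3.2 defines a prior medicine as one starting before the date and time of first dose. Among the Day 225 summaries it lists "Concomitant medications that were started on or after the first dose of investigational product by ATC level 2 and preferred term" (Table 14.1.4.3 in Appendix 1).

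**Background therapy.** Protocol 6.1, criterion 3: "Subject has received entecavir or tenofovir for at least 2 years with a stable dose for at least 6 months prior to screening". The flow charts in both documents record concomitant medication at screening.

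**The concern.** Adverse events are recorded from the screening visit (Protocol 9.2), so the start date decides whether an event is treatment-emergent. Unsolicited AEs through Day 85 are a primary variable (SAP 7.1). Two programmers could each follow the SAP and classify the same undated event differently. On the literal reading of 14.3 the event has no date to compare with the window, and no default sends it either way. That is out of line with the rest of section 14, where a missing relationship becomes possibly related (14.5) and a missing severity on or after first dose becomes severe (14.4).

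For medicines the rule is clear but can contradict what the trial already knows. A medicine written down at screening began before the first injection. If its start date is blank and it is ongoing, the rule places it among medicines begun on or after first dose. For entecavir or tenofovir (the background nucleos(t)ide, NUC) this also contradicts an inclusion criterion.

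**Working it through.** The plan states no figure on this point. The check is to follow the rules through test cases.

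**Inputs.** Start-date rules: SAP 14.2.1 and 14.2.3. TEAE window: SAP 12.6.1. Prior-medicine definition: SAP 12.3.2. NUC duration: Protocol 6.1. Arm size of 10: SAP 6.1. Assumed for illustration only: first dose on 15 Jun 2017 at 10:00.

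**1. AE with no start date and no start time.**
- *14.3 read literally, with 14.0:* no date is assigned. The event cannot be compared with the first dose or with the end of the window (last dose plus 30 days, nominally Day 57 + 30 = Day 87). If its severity is also missing, 14.4 cannot choose between mild and severe, because that choice depends on the start date.
- *14.3.1, then 14.2.1.1 and 14.2.3:* onset becomes 15 Jun 2017 10:00, exactly the dosing time, so onset minus dosing time = 0. If the window means at or after the first dose, the event is a TEAE. If it means strictly after, it is not.
- *The same route with a complete stop date before first dose:* onset becomes the stop date, and the event is before treatment.

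So an undated event with no earlier stop date can be unclassified, a TEAE or not a TEAE, depending on which line is followed and how the window is read. The zero-difference problem also affects partial dates that 14.2.1 sets to the dosing date when the time is missing.

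**2. Month missing, day and year known.** Start dates have three branches: everything missing (14.2.1.1), day and month missing (14.2.1.2), day only missing (14.2.1.3). Stop dates have four, including month only (14.2.2.3). A start date lacking only its month is partially missing, so 14.3 promises imputation, but no rule supplies it.

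**3. Medicines.**

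| Start date known | Stop | Imputed start | Class |
|---|---|---|---|
| Nothing | ongoing | 15 Jun 2017 10:00 | not prior; on or after first dose |
| Nothing | 1 Mar 2017 | 1 Mar 2017 | prior |
| Year 2014 | ongoing | 31 Dec 2014 | prior |
| Year 2015 | ongoing | 31 Dec 2015 | prior |
| Year 2017 (dosing year) | ongoing | 15 Jun 2017 10:00 | not prior; on or after first dose |
| April 2017 | ongoing | 30 Apr 2017 | prior |

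Rows 1 and 5 are wrong for any medicine already recorded at screening. A NUC taken for at least 2 years would not normally fall in row 5, because its start year lies before the dosing year. It is misdated only in row 1, when even the year is unknown.

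**4. Size.** One subject in an arm of 10 is 1/10 = 10 percentage points. Overall TEAE incidence moves by that amount only if the undated event is the subject's sole TEAE. Otherwise only the tables by system organ class and preferred term, and the event counts, change.

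**The case against.** The strongest reply is that 14.3.1 settles the matter. The SAP files the wholly missing case under its incomplete-date heading and applies that section to AEs without exception, so a programmer would impute the first-dose date. That is a reasonable reading, but 14.3 itself defines incomplete as partially missing, and nothing says which line governs.

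There are also real safeguards. Onset date and time are to be recorded for every AE (Protocol 9.2). Database checks raise queries (Protocol 11.2). The blinded data review covers missing data and finalises the SAP (SAP 11.3). All AEs are listed, and SAEs and AESIs are summarised whether or not they are treatment-emergent (SAP 12.6.1). These make undated events rare and protect the most important ones. They do not say how a remaining undated event is classified.

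Two stronger readings are tempting, and the documents support neither:
- *Undated AEs drop out of the TEAE tables.* A reader might infer this from 14.3, but no line states it and 14.3.1 points the other way. It is one outcome of a contradiction.
- *The table of medicines begun after vaccination fills with long-standing NUC therapy.* This needs NUC records without even a start year, which is unlikely when eligibility requires at least 2 years of treatment. The documents give no count of such records, and any percentage would be a guess.

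For medicines, the consequence is limited further. The drug is still counted as concomitant, SAP 12.3.2 assigns the before/after split to the Day 225 analysis, and NUC exposure is tabulated separately (Protocol 10.8.1).

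**Conclusion.** The point stands as an inconsistent and incomplete set of date rules, and it should be corrected. For AEs, 14.3 and 14.3.1 disagree on wholly missing start dates, and 14.2.1 gives no result when only the month is missing. An onset imputed to the dosing time meets the TEAE definition on one reading and fails it on another. For medicines, the rule is wrong as written for an ongoing medicine known from screening with no start date. It is also wrong when only the year is known and that is the dosing year. The error is confined to the split at first dose.

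The practical effect is probably small. It depends on how many records lack dates after query resolution, which the documents do not give. The upper bound for one subject is 10 percentage points of an arm's TEAE incidence, under the sole-TEAE condition. The reason to act is that the rule governs a primary safety summary and is best settled before unblinding.

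**What to change.** 1. In SAP 14.3, state that partially and wholly missing AE start dates both follow 14.2.1, keeping its stop-date guard. State also that an AE whose imputed onset equals the first-dose date and time counts as treatment-emergent.
2. Add a month-only branch to 14.2.1, for instance by setting the known day aside and applying 14.2.1.2.
3. In 14.2.1, for medicines, class anything recorded at screening or before the Day 1 injection, and the background NUC, as started before first dose when its start date is missing. Apply the same to a partial date that the rules would otherwise move to the dosing date. Use the first-dose date only for medicines first recorded afterwards.

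The cost is a few lines of text and a small program change, which the two-stage SAP process (SAP 4.0) allows before database lock. The downside is that a few undated AEs may be counted as treatment-emergent when they were not. The stop-date guard limits this, and the direction matches the defaults for missing relationship and post-dose severity.

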#### 14.3.1 Incomplete Start Date and time

Follow same rules as in [section 14.2.1](#) and [section 14.2.3](#).

#### **14.4 Missing Severity Assessment for Adverse Events**

If severity is missing for an AE starting prior to the date of the dose of investigational product, then a severity of "Mild" will be assigned. If the severity is missing for an AE starting on or after the date of first dose of investigational product, then a severity of "Severe" will be assigned. The imputed values for severity assessment will be used for incidence summaries, while the actual values will be used in data listings.

#### **14.5 Missing Relationship Assessment for Adverse Events**

If relationship to product is missing for an AE, then a relationship of "Possibly related" will be assigned. The imputed values for relationship assessment will be used for incidence summaries, while the actual values will be used in data listings.

### **15.0 Validation**

PRA's goal is to ensure that each TFL delivery is submitted to the highest level of quality. Our quality control procedures will be documented separately in the study specific quality control plan.

## Appendix 1 Tables, Figures, Listings, and Supportive SAS Output Appendices

List of Post-Text Tables, Figures, Listings, and Supportive SAS Output Appendices:			
Output	Title 1	Title 2	Top Line
Table 14.1.1.1	Disposition	All Screened Subjects	
Table 14.1.1.2	Important Protocol Deviations	Randomised Set	
Table 14.1.2.1	Demographic Characteristics	Safety Analysis Set	X
Table 14.1.2.2	Demographic Characteristics	Full Analysis Set	
Table 14.1.2.3	Demographic Characteristics	Immunogenicity Analysis Set	
Table 14.1.3	Medical History by System Organ Class and Preferred Term	Safety Analysis Set	
14.1.4.1	Concomitant Medications by WHO Drug Dictionary Preferred Term	Safety Analysis Set	
Table 14.1.4.2	Concomitant Medications that Began Before First Dose of Investigational Product	Safety Analysis Set	
Table 14.1.4.3	Concomitant Medications that Began on or After First Dose of Investigational Product	Safety Analysis Set	
Table 14.2.1.1	ELISPOT Score results by Peptide and Time point – Ex-vivo Assay	Immunogenicity Analysis Set	
Table 14.2.1.2	ELISPOT Score results by Peptide and Time point – Cultured Assay	Immunogenicity Analysis Set	
Table 14.2.1.3	ELISPOT Score results by Peptide and Time point – Ex-vivo Assay	Full Analysis Set	
Table 14.2.1.4	ELISPOT Score results by Peptide and Time point – Cultured Assay	Full Analysis Set	X
Table 14.2.1.5	Sum ELISPOT Score results by Time point – Ex-vivo Assay	Immunogenicity Analysis Set	
Table 14.2.1.6	Sum ELISPOT Score results by Time point – Cultured Assay	Immunogenicity Analysis Set	
Table 14.2.1.7	Sum ELISPOT Score results by Time point – Ex-vivo Assay	Full Analysis Set	
Table 14.2.1.8	Sum ELISPOT Score results by Time point – Cultured Assay	Full Analysis Set	X
Figure 14.2.1.9	Line Plot of Mean ( $\pm$ SE) ELISPOT Score against Time by Treatment Group and Peptide – Cultured Assay	Immunogenicity Analysis Set	
Figure 14.2.1.10	Line Plot of Mean ( $\pm$ SE) ELISPOT Score against Time by Treatment Group and Peptide – Cultured Assay	Full Analysis Set	

Figure 14.2.1.11	Line Plot of Individual Subjects' ELISPOT Score against Time by Treatment Group and Peptide – Cultured Assay	Immunogenicity Analysis Set	
Figure 14.2.1.12	Line Plot of Individual Subjects' ELISPOT Score against Time by Treatment Group and Peptide – Cultured Assay	Full Analysis Set	
Table 14.2.2.1	Quantitative Virology Results by Time Point - HBsAg and HBV DNA	Immunogenicity Analysis Set	
Table 14.2.2.2	Qualitative Virology Results by Time Point - HBsAb	Immunogenicity Analysis Set	
Table 14.2.2.3	Quantitative Virology Results by Time Point - HBsAg and HBV DNA	Full Analysis Set	X
Table 14.2.2.4	Qualitative Virology Results by Time Point - HBsAb	Full Analysis Set	
Figure 14.2.2.5	Line Plot of Change from Baseline in log10 HBsAg at each Timepoint by Treatment Group	Immunogenicity Analysis Set	
Figure 14.2.2.6	Line Plot of Change from Baseline in log10 HBsAg at each Timepoint by Treatment Group	Full Analysis Set	
Table 14.3.1.1	Summary of Investigational Product Exposure	Safety Analysis Set	
Table 14.3.2.1	Overall Summary of Adverse Events	Safety Analysis Set	
Table 14.3.2.2	Treatment-emergent Adverse Events by System Organ Class and Preferred Term	Safety Analysis Set	X
Table 14.3.2.3	Treatment-emergent Adverse Events by System Organ Class and Maximum Severity	Safety Analysis Set	
Table 14.3.2.4	Serious Adverse Events by System Organ Class and Preferred Term	Safety Analysis Set	
Table 14.3.2.5	Possibly Treatment-Related Treatment-emergent Adverse Events by System Organ Class and Preferred Term	Safety Analysis Set	
Table 14.3.2.6	Serious Possibly Treatment-Related Adverse Events by System Organ Class and Preferred Term	Safety Analysis Set	
Table 14.3.2.7	Possibly Treatment-Related Treatment-emergent Adverse Events by System Organ Class and Maximum Severity	Safety Analysis Set	
Table 14.3.2.8	Treatment-emergent Adverse Events leading to Discontinuation of Investigational Product by System Organ Class and Preferred Term	Safety Analysis Set	
Table 14.3.2.9	Adverse Events with Fatal Outcome by System Organ Class and Preferred Term	Safety Analysis Set	
Table 14.3.2.10	Adverse Events of Special Interest by System Organ Class and Preferred Term	Safety Analysis Set	
Table 14.3.3.1.1	Haematology Results by Time Point	Safety Analysis Set	
Table 14.3.3.1.2	Investigator Assessed Clinically Significant Postbaseline Haematology Results	Safety Analysis Set	
Table 14.3.3.1.3	Shift Summary of Haematology Results by Reference Range and Time Point	Safety Analysis Set	

Table 14.3.3.2.1	Biochemistry Results by Time Point	Safety Analysis Set	
Table 14.3.3.2.2	Investigator Assessed Clinically Significant Postbaseline Biochemistry Results	Safety Analysis Set	
Table 14.3.3.2.3	Shift Summary of Biochemistry Results by Reference Range and Time Point	Safety Analysis Set	X
Table 14.3.3.3.1	Quantitative Urinalysis Results by Time Point	Safety Analysis Set	
Table 14.3.3.3.2	Investigator Assessed Clinically Significant Postbaseline Urinalysis Results	Safety Analysis Set	
Table 14.3.3.3.3	Shift Summary of Quantitative Urinalysis Results by Time Point	Safety Analysis Set	
Table 14.3.4.1	Vital Signs Results by Time point	Safety Analysis Set	
Table 14.3.5.1	Shift Summary of Investigator's ECG Interpretation	Safety Analysis Set	
Table 14.3.6.1	Incidence of Investigator Assessed Injection Site Reactions	Safety Analysis Set	
Table 14.3.6.2	Incidence of Investigator Assessed Injection Site Reactions by Severity and Time point	Safety Analysis Set	
Table 14.3.6.3	Incidence of Subject Assessed Injection Site Reactions by Severity and Time point – Diary Card Data	Safety Analysis Set	X
Table 14.3.6.4	Incidence of Investigator Assessed Injection Site Reactions by Maximum Severity and Time point	Safety Analysis Set	
Table 14.3.6.5	Incidence of Subject Assessed Injection Site Reactions by Maximum Severity and Time point	Safety Analysis Set	
Listing 16.1.7	Randomisation Assignments	Randomised Set	
Listing 16.2.1.1	Screening Information	All Screened Subjects	
Listing 16.2.1.2	Subject Disposition	Randomised Set	
Listing 16.2.1.3	Discontinued Subjects	Randomised Set	
Listing 16.2.2	Protocol Deviations	Randomised Set	
Listing 16.2.3	Subject Analysis Sets	Randomised Set	
Listing 16.2.4.1	Demographic and Baseline Data	Randomised Set	
Listing 16.2.4.2	Fibroscan Results at Screening	Randomised Set	
Listing 16.2.4.3	Drugs of Abuse at Screening	Randomised Set	

Listing 16.2.4.4	Virology Results at Screening	Randomised Set
Listing 16.2.4.5	General Medical History	Randomised Set
Listing 16.2.4.6	Prior and Concomitant Medications	Randomised Set
Listing 16.2.5.1	Investigational Product Administration	Safety Analysis Set
Listing 16.2.6.1	Laboratory Test Results – Gamma Interferon (IFN- $\gamma$ ) ELISPOT	Full Analysis Set
Listing 16.2.6.2	Laboratory Test Results – Virology Parameters	Full Analysis Set
Listing 16.2.7.1	Adverse Events	Safety Analysis Set
Listing 16.2.7.2	Serious Adverse Events	Safety Analysis Set
Listing 16.2.7.3	Adverse Events Considered Possibly Related to Investigational Product	Safety Analysis Set
Listing 16.2.7.4	Adverse Events Leading to Discontinuation of Investigational Product	Safety Analysis Set
Listing 16.2.7.5	Adverse Events with Fatal Outcome	Safety Analysis Set
Listing 16.2.7.6	Adverse Events of Special Interest	Safety Analysis Set
Listing 16.2.8.1	Laboratory Haematology Results and Change from Baseline	Safety Analysis Set
Listing 16.2.8.2	Laboratory Biochemistry Results and Change from Baseline	Safety Analysis Set
Listing 16.2.8.3	Laboratory Urinalysis Results and Change from Baseline	Safety Analysis Set
Listing 16.2.8.4	Pregnancy Test Results (Females of Childbearing Potential Only)	Safety Analysis Set
Listing 16.2.9	Vital Signs (Sitting)	Safety Analysis Set
Listing 16.2.10	Electrocardiogram Results	Safety Analysis Set
Listing 16.2.11.1	Injection Site Tolerability – Investigator Assessed	Safety Analysis Set
Listing 16.2.11.2	Injection Site Tolerability – Diary Card	Safety Analysis Set
Listing 16.2.12	Physical Examination Results	Safety Analysis Set
Listing 16.2.13	Telephone Calls	Safety Analysis Set
Listing	Legacy Data not Required by Protocol	Randomised Set

Sponsor: Altimune UK Ltd

Protocol no: FP02.2\_CS\_01

Statistical Analysis Plan

09-Mar-2018

16.2.14

